- Compare monthly RDT consumption data and volumes/TPRs reported via the registers and HMIS/DHIS2 with manual counts of used RDTs and RDT positives collected from health facilities and CHWs in monthly counts. A digital tool will be used alongside the manual counting process to take pictures of each RDT counted and provide the RDT test result.
- Identify discrepancies between reported and manual RDT counts, TPRs and ACT consumption and discuss these in monthly validation meetings.
- Observe whether discrepancies will disappear over time:

⁸ Cameroon National Malaria Control Program annual report, 2022.

⁹ Cameroon DHIS2, 2022

- Manually and digitally counted RDT volumes and positives converge with what is reported in registers/DHIS2
- Manually and digitally country RDTs and RDT positives will converge with reported RDT and ACT consumption volumes
- Assess operational feasibility, costs, and acceptability of the manual RDT storage and count method.

Participating health care workers and CHWs in study sites will be informed about the manual count and asked to store all used RDTs in labeled storage containers that will be provided for this purpose. HCW/CHW are expected to conduct business as usual, interpreting and reporting RDTs per national guidelines and recording the RDT results. At the end of each month, supervisors will collect and count the RDTs. The number of positive and total RDTs will be manually recorded and totals will be compared with the register and DHIS2 reported RDT country and positives.

Primary outcome:

• The primary outcome will be a comparison of the volume and test positivity rate (TPR) from the manual counts by trained supervisors to the TPR recorded in the HMIS (historic, surrounding areas, by CHWs and HF) on a monthly basis over the course of the 6-month intervention.

Secondary:

The secondary outcomes of this study are to:

- 1. Compare the manually counted RDTs and RDT positives to what was recorded in the registers
- 2. Compare the manually counted RDTs and RDT positives to the consumption of RDTs and ACTs recorded in the DHIS2 and pharmacy records (i.e., supply log)
- 3. Compare the costs of implementing the monthly RDT validation with potential savings from reductions in prescription of ACTs
- 4. Measure the impact of monthly RDT validation exercises on changes in HCWs' subjective norms, attitudes, perceptions and practices related to RDTs

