In Depth Interviews with participants will be conducted in designated private spaces. If a private space is not available, an alternate location will be used to maintain confidentiality. Interviews will be audio recorded, transcribed verbatim in English language. Personal identifiers such as names and phone numbers will only be collected during the informed consent process and will not be recorded during interviews. The names of health facilities will be collected during data collection for identification purposes but will be excluded during data cleaning to ensure confidentiality.

To minimize risk of disclosure to others and discrimination or stigmatization, measures will be taken to avoid loss of confidentiality. A unique identification number will be assigned to all participants. Access to the completed study instruments and databases will be limited to the project manager, project lead, and data analysts. All data files will be password - protected.

Data analysis

1. Quantitative analysis

The primary outcome will be assessed with a chi-squared test to analyze whether the difference between reported TPR and counted TPR is significantly significant. This will include outcomes for an average across all surveyed points of care (POCs), disaggregated by HFs and CHWs, and compared between baseline (pre-intervention) and endline (after six months of the intervention).

We will further investigate the difference and change in TPR by constructing a mixed effects linear regression model with the POC-month as the unit of analysis and TPR as the outcome variable. The model will include a binary indicator to exhibit pre/post intervention (implementation of the RDT check), a binary variable to indicate intervention group (i.e. "reported" or "counted" TPR), a dummy variable to exhibit month since introduction of the intervention, and a random effect variable for POC type to account for clustering. 95% confidence intervals will be fit around the TPR per POC-month.

To determine whether changes in TPR were due to changes in provider behavior or changes to the DHIS2 data, the ratio of TPRs from the health facility register to the RDT cassettes will be plotted over the six months of the intervention and compared to the change in TPR reported from the DHIS2 data.

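### The aim is to see whether reported and counted figures converge, but the only named test of the TPR gap is a test of difference, which cannot show that the gap has gone

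*Protocol*

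**What the plan says.** Under AIM and Outcomes, one specific aim is to "Observe whether discrepancies will disappear over time". Its sub-items speak of counted volumes and positives converging with registers and DHIS2, and with reported RDT and ACT consumption. Neither word is given a criterion.

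Under Data analysis, 1. Quantitative analysis, the protocol states: "The primary outcome will be assessed with a chi-squared test to analyze whether the difference between reported TPR and counted TPR is significantly significant". This is done overall and split by health facilities (HFs) and community health workers (CHWs), and "compared between baseline (pre-intervention) and endline (after six months of the intervention"). The length of the endline window is not given.

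Three further looks at the data are planned in the same section:
- "constructing a mixed effects linear regression model with the POC-month as the unit of analysis and TPR as the outcome variable", with terms for pre/post, source (reported or counted) and month, and a random effect for type of point of care (POC);
- "95% confidence intervals will be fit around the TPR per POC-month";
- "the ratio of TPRs from the health facility register to the RDT cassettes will be plotted over the six months of the intervention", to be compared with the change in DHIS2 TPR.

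Under Sampling calculation, the study is sized for TPR falling from 65% to 40% in HFs and from 95% to 50% in CHWs, at 5% type 1 error, 80% power and an ICC of 0.05. The result is 2121 HF and 1292 CHW tests over six months.

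**The concern.** Convergence is a claim of agreement: the remaining gap is small enough to ignore. A chi-squared test takes no gap as its null hypothesis, so failing to reject it may mean agreement or may mean too few tests. A significant result at baseline beside a non-significant one at endline also does not show that the gap shrank.

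The sizing does not help, because it targets differences of 25 and 45 points, not the exclusion of a small residual gap.

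The results are meant for the national programme and for policy briefs on scale-up. If convergence were inferred from a p-value, over-reporting could be described as removed while several points of it remained. The stratum with fewer tests, the CHWs, would reach non-significance most easily, although the sizing assumes the largest inflation there.

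**Working it through.** **1. The plan's own sizes.** The usual pooled two-proportion formula (two-sided 5%, 80% power, no clustering) gives 62 tests per group for 65% vs 40% and 15 for 95% vs 50%. The cluster size behind the design effect is not stated, so 2121 and 1292 cannot be reproduced. Taking m = 2121/16 = 133 and 1292/31 = 42, the design effects 1 + (m − 1) × 0.05 are 7.58 and 3.03. Totals for both groups are then 2 × 62 × 7.58 = 940 and 2 × 15 × 3.03 = 91. The point below does not depend on this; it takes 2121 and 1292 as stated.

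**2. Tests in an endline month at those minimums.** 2121/6 = 354 (HF) and 1292/6 = 215 (CHW).

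**3. Chance that the test misses a real gap.** Inputs: counted TPR 40% (HF) and 50% (CHW), the protocol's expected values; two-sided 5% (sidedness is not stated); n tests per source, treated as independent, no clustering. The gap d is illustrative.

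Power ≈ Φ[(d − 1.96 × s0)/s1], with s0 = √(2p̄(1 − p̄)/n) and s1 = √((p1(1 − p1) + p2(1 − p2))/n).

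- HF, one month, 40% vs 45%: s0 = 0.0372, s1 = 0.0371; the argument is −0.62, power 27%, missed 73%.
- CHW, one month, 50% vs 55%: s0 = 0.0482, s1 = 0.0481; the argument is −0.92, power 18%, missed 82%.
- HF, six months pooled: s0 = s1 = 0.0152; the argument is 1.34, power 91%, missed 9%.
- CHW, six months pooled: s0 = s1 = 0.0196; the argument is 0.59, power 72%, missed 28%.

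| Window at minimum volume | n per source (HF / CHW) | 5-point gap missed (HF / CHW) | 10-point gap missed (HF / CHW) |
|---|---|---|---|
| One month | 354 / 215 | 73% / 82% | 24% / 45% |
| Six months pooled | 2121 / 1292 | 9% / 28% | under 1% / under 1% |

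If real monthly volume were two or three times the minimum, the HF one-month figure would be 52% (708 tests) or 36% (1062). At three times the minimum the CHW figure would be 56% (645).

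**4. What a non-significant month would leave open.** The half-width of the 95% CI on the gap, 1.96 × √(2p(1 − p)/n), is 7.2 points (HF) and 9.5 points (CHW) for one month, and 2.9 and 3.9 points for six months.

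**5. Sensitivity to pairing.** Both TPRs may describe the same cassettes, so independence is doubtful. In a simulation on shared cassettes, the unpaired chi-squared test at one month detected a 5-point gap only 3–13% (HF) and 0.3–5% (CHW) of the time, depending on how much other disagreement was assumed. McNemar's test detected it 69–100% and 49–100% of the time. Over six months the unpaired test detected it 99–100% and 87–98% of the time.

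**6. Whether another planned analysis fills the gap.**
- The source term in the model gives an average reported-counted difference over the months modelled. No listed term lets that difference change with time, so it is not the gap at the end.
- The intervals are on each TPR, not on the difference.
- The ratio is plotted, with no interval mentioned, and covers the register and the cassettes only.

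**The case against.** The strongest reply is that the protocol contains no rule equating non-significance with convergence. The verb in the aim is to observe, the study is an observational pilot, and the chi-squared test is attached to the primary outcome rather than to the convergence items. Some of those items concern volumes and consumption, which a TPR test cannot address. This stands. A reader might infer that the plan will declare convergence when the endline test is non-significant; the document does not say so.

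It also stands that the chi-squared test is not the only look at the gap. The model has a source term, the ratio plot follows the gap descriptively, and counts are compared and fed back each month. A gap of 5 to 10 points could be visible there whatever the p-value. None of these, however, states how large a gap the final data still allow.

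A reader might also infer that the study will usually miss a 5-point gap. That holds for a one-month endline at minimum volume. It fails for six months pooled, and the minimums are expected to be met easily in HFs.

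Finally, a convergence margin could be set in a separate analysis plan, so its absence alone is not a fault. What remains is that the protocol itself names the test, and that kind of test cannot answer this aim.

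**Conclusion.** The point holds as a mismatch between aim and method. The protocol asks whether a gap closes and names only a test of whether a gap exists. No listed analysis estimates the endline gap with its uncertainty.

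The size depends on an undefined window: a 5-point gap is missed 73% (HF) and 82% (CHW) of the time for one month at minimum volume, and 9% and 28% for six months pooled. These figures assume independent samples, no clustering, counted TPRs of 40% and 50%, and a gap chosen for illustration. Pairing changes them greatly, so they show the scale of the problem and do not predict this study's error rate. The change is worth making before the first count. It does not rest on any claim that the investigators intend to read a p-value as convergence.

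**What to change.** - Define the endline window (for example, the last month or the last two).
- For HFs and CHWs separately, report the reported-minus-counted TPR difference for that window with a 95% CI computed from POC-level paired differences, so that pairing and clustering are respected. Where DHIS2 holds CHW figures only for the group attached to a facility, pair at that level.
- Base any statement about convergence on that interval: either give the largest gap still compatible with the data, or require the whole interval to lie within a margin that the sponsor fixes before the first count.
- State that a non-significant chi-squared result will not be described as convergence.

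This costs a few sentences and no new data. The downside is that convergence becomes harder to claim. Purely as an illustration, take a 5-point margin, a true gap of zero, independent samples and 80% power. Placing a 95% CI inside the margin then needs 2p(1 − p)(1.96 + 1.28)²/0.05² ≈ 2018 tests per source in HFs and 2102 in CHWs. One month at minimum volume falls well short in both groups; six months reaches it for HFs (2121) but not for CHWs (1292). Pairing may improve on this, but CHW results may have to be reported as inconclusive.

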All health workers (n=32 - 2 per HF) and CHWs (n=31) in the Garoua Boulai health district will be approached for consent and included in the study. We anticipate collecting a minimum of 2121 tests conducted during the study period in outpatients and 1292 tests conducted in the community by polyvalent CHWs.

Inclusion/Exclusion Criteria

PARTICIPANTS- health workers in participating health facilities and CHWs in health areas (catchment) tasked to conduct the malaria RDT in patients suspected of having malaria

INCLUSION CRITERIA:

- All RDTs conducted in outpatients suspected of having malaria by participating CHWs in the targeted health area
- All RDTs conducted by participating healthcare workers on patients at the HFs
- All healthcare workers and community health workers that provided consent to participate in the study

EXCLUSION CRITERIA:

- RDTs conducted by CHWs on pregnant women (Because tests from pregnant women carried out by CHWs are not recorded in the DHIS2) or in patients
- Nonconsenting HCWs

Study Design

This is an observational pilot conducted over six months in the Garoua-Boulaï Health District. It will involve 16 health facilities and 31 CHWs routinely performing malaria testing. The selected district was selected because (i) historic testing data would suggest we could easily meet the sample size of 2121 tests in a period of 6 months in the HFs, (ii) the research team already has ongoing operations in the district, (iii) CHWs carry out Integrated Community case management (ICCM). In collaboration with district health officials and the nurse in charge of the participating health facilities, the health workers, supervisors and the community health workers in the district that conduct malaria RDTs will be invited to a short training in which the study will be explained. The health workers will be informed of the manual count of the RDTs and equipped with containers for storage of the used RDTs. They will be requested to store the used RDT readers be it positive or negative. Supervisors will collect the stored readers monthly for the manual and digital review and counting. Discrepancies will be communicated back to

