nurses in charge of the participating health facilities after each count. The supervisors and the district health official will participate in the monthly count process, facilitated and chaired by the research team (at least for the first few months). Participants in the counting process will receive brief training on manual RDT result interpretation by the research team and use of the digital tool (a mobile app downloaded on a phone).

Sampling calculation

We hypothesize that the TPR recorded in the registers differs from the TPR found through the manual count and used the anticipated difference in our sample size calculations. We calculated sample size requirements based on a cluster randomized two-sample unpaired t-test for the comparison of two proportions using standard formulae (Hayes and Bennett, 1999). We fixed the Type 1 error at 5% and the power at 80%. Prior to the intervention we assume the TPR to be 65% in HFs and 95% in CHWs. We hypothesize that this, as a result of our intervention, will decrease to 40% in HFs and 50% in CHWs. We accordingly calculated separate sample sizes for HFs and CHWs based on the baseline and expected proportions. Since we will be sampling HFs and CHWs, we expect that there will be clustering effects in the populations that these Point Of Care serve. As such, we took clustering into account by applying a design effect based on the total population (i.e. total number of tests) that these POCs cover over six months (the assumed sampling time period) - using 2023 testing data for all HFs and CHWs in East region. We used an ICC of 0.05. Based on these assumptions and calculations, the maximum sample size required for HFs and CHWs respectively is 2121 and 1292 tests. We aim to sample from 16 HFs and 31 CHWs over a single district in the East region to control unknown confounders and differences in behavior/population between HFs and CHW catchment populations.

Tools for data collection

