2	Secondary	The proportion of RDTs reported as positive in months prior to intervention and in surrounding HF and CHWs	TPR calculated during the monthly validation meetings will be compared to the TPR found in the DHIS2 of HF in surrounding districts and in the TPR of intervention HF and CHWs attached to that HF in the same month in the three previous years.
		The total number of positive RDT found in the manual count and the total volume of ACTs administered	The total count of positive RDTs during the monthly validation meeting for each HF and CHWS attached to the HF will be compared to the total count of ACTs administered at that HF and by CHW attached to that HF during the same period, as recorded in the institution's supply log.

Total costs associated with monthly RDT counts	Collection and analysis of cost data, including personnel costs, travel expenses, and other project-related expenses will be used to estimate the total costs associated with the RDT counts
HCWs subjective norms, attitudes, perceptions and practices regarding RDT usage	A survey will be administered to participating HCWs to understand their subjective norms, attitudes, perceptions and practices regarding RDT
Acceptability and feasibility of implementing monthly RDT validation exercises	In-depth interviews will be conducted with HCWs, health officials to understand their perceptions of the acceptability of the monthly validation processes

Potential Risks

We do not foresee direct risks to participants in the study. One potential risk would be in health outcomes if fewer ACTs are administered. In Benin, where the manual count has already been rolled out, no significant impacts were recorded related to increases in morbidity and mortality in the intervention areas. The proposed intervention would not deviate from existing national guidelines in which ACTs should only be administered to patients with a parasite-based positive diagnosis (i.e., microscopy or RDT).

Loss or damage of RDT cassettes before validation is a potential risk to the study fidelity. As a mitigation, an SOP for proper storage of RDT cassettes will be provided to participating health workers for the safe handling and retention. Regular checks, especially in the first few months will also be conducted to ensure adherence to storage protocols.

Participant Enrollment and informed consent

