To ensure compliance with study protocols, monthly CHW and health facility supervision visits will be conducted throughout the study period. These visits will serve to verify all used RDTs are stored and labelled appropriately using the designated collection devices, to troubleshoot any issues around RDT storage, to copy (or bring) the registers for the review period, and to transport the cassettes for the count. Informed, written consent will be obtained from all participants involved in the in depth interviews and qualitative survey. Participants will be

informed that their participation is entirely voluntary and that they are under no obligation to participate if they do not wish to. They will be assured that no negative consequences will result from their decision to either participate or decline. They will also be informed that they have the right to withdraw from the study at any point, without facing any repercussions. Confidentiality will be maintained throughout the study.

Since all participants are expected to be literate, written consent will be feasible and preferred. Should any exceptions arise, alternative methods of obtaining consent (such as oral consent witnessed by a third party) will be considered, ensuring the process remains ethical and transparent.

Data collection and SUBJECT CONFIDENTIALITY

Strict measures will be taken to ensure the confidentiality of all data collected during the study. All quantitative data collection activities will be carried out using smartphones equipped with Open Data Kit (ODK) tools and the research team will be trained on the data collection processes. The tools will be implemented using a smartphone which will be provided to all research assistants.

Participant confidentiality will be maintained during the intervention. No patient identifying information will be collected. Results will be reviewed in aggregate by CHWs and health facility Data will be stored in secured registers. The data will only be accessible to the Data Manager and the PI. It will be reviewed regularly to ensure quality and completeness. Only fully deidentified data will be provided to other study personnel or statisticians. Only fully deidentified data will be shared.

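### No described step separates the excluded CHW cassettes at the count, and ACTs are set against RDT positives alone, so volume and ACT gaps can appear without any misreporting

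*Protocol*

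**What the plan says.** **CHW tests on pregnant women.** The protocol's Inclusion/Exclusion Criteria exclude them, giving as the reason that "tests from pregnant women carried out by CHWs are not recorded in the DHIS2". Under AIM and Outcomes, workers are "asked to store all used RDTs in labeled storage containers". Under Participant Enrollment and informed consent, the monthly visits verify that all used RDTs are stored and labelled. Under Data collection and SUBJECT CONFIDENTIALITY: "No patient identifying information will be collected". The count is compared each month with DHIS2 and the registers, and as a secondary outcome with RDT and ACT consumption.

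**ACTs.** In Study Outcome Measures, the month's positive RDTs for each facility and its CHWs "will be compared to the total count of ACTs administered at that HF and by CHW attached to that HF during the same period". Potential Risks says national guidelines reserve ACTs for patients with "a parasite-based positive diagnosis (i.e., microscopy or RDT").

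**Who and which patients at facilities.** The facility inclusion line reads "All RDTs conducted by participating healthcare workers on patients at the HFs". Study population approaches "All health workers (n=32 - 2 per HF) and CHWs (n=31") for consent but describes the facility target of 2121 tests as tests in outpatients. The exclusion list names non-consenting workers, and its CHW bullet ends with a reference to in-patients.

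**The concern.** The main comparison is a reconciliation: cassettes on one side, reported or dispensed totals on the other. A gap can be read as misreporting or as irrational ACT use only if both sides cover the same tests. In two places the text fixes different sets.

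First, the exclusion of pregnant women is meant to align the CHW count with DHIS2, but nothing described makes it workable at the counting table. The excess it leaves would look like CHWs under-reporting their tests. Second, an ACT given after positive microscopy has no cassette behind it, so it would look like an ACT given without a positive test.

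Discrepancies go back to the nurses in charge after each count, and the study looks for them to disappear over time. A gap that does not come from reporting behaviour cannot be closed by changing that behaviour.

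**Working it through.** The plan gives no figure for unmatched tests, so there is none to reproduce on this point. Its sample sizes serve below only for scale. The two-proportion formula (5% two-sided, 80% power) gives 62 per group for 65% against 40% and 15 per group for 95% against 50%. Reaching 2121 and 1292 from there needs the number of tests per point of care, which is not stated. Those totals are therefore neither confirmed nor refuted, and nothing below depends on them.

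1. **Excluded CHW cassettes left in the count.** Let q be the share of all CHW tests done on pregnant women. The documents do not give it; 5% to 15% is an illustrative assumption. If reporting is perfect and no cassette is lost, cassettes / DHIS2 tests = 1/(1−q), so the excess is q/(1−q).
   - q = 5%: 0.05/0.95 = 5.3%
   - q = 10%: 0.10/0.90 = 11.1%
   - q = 15%: 0.15/0.85 = 17.6%

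   For scale, if 1292 eligible tests were recorded, the pile would hold 1292/0.95 = 1360 cassettes (68 too many) at 5%, and 1292/0.85 = 1520 (228 too many) at 15%.

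2. **The same cassettes removed.** The count now agrees with DHIS2, but RDTs consumed by CHWs exceed RDTs counted by the same q/(1−q). CHW ACT totals still include any ACTs given to these women. Nothing in the text removes them from the consumption side.

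3. **TPR effect of step 1.** With TPR p in eligible tests and r in the extra ones, the gap is q(r−p), which is zero when r = p. Take q = 10% and p = 50% (the plan's expected CHW value):
   - r = 70%: 0.10 × 20 = 2 points; unpaired chi-squared 1.09
   - r = 90%: 0.10 × 40 = 4 points; chi-squared 4.36, above 3.84

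   Since |r−p| cannot exceed 1, the gap can never exceed q. At q = 15% it is below 15 points, against a hypothesised CHW difference of 95 − 50 = 45.

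4. **ACTs at health facilities.** Let m be the share of tested patients examined by microscopy, with positivity p by either method and one ACT course per positive. ACTs = Np and RDT positives = N(1−m)p, so the excess is 1/(1−m) − 1 = m/(1−m).
   - m = 10%: 1/0.90 − 1 = 11%
   - m = 31%: 1/0.69 − 1 = 45%

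   The 31% is 100% minus the national 69% RDT share in the background section. Using it assumes that the whole remainder is microscopy and that the national figure applies to this district. If microscopy positivity were half that of RDTs, the excess would halve: 0.5 × 0.111 = 5.6% and 0.5 × 0.449 = 22%.

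5. **Non-consent (conditional).** With 32 workers, two per facility and equal workload, one refusal removes 1/32 = 3.1% of facility cassettes. DHIS2 then exceeds the count by 0.03125/0.96875 = 3.2% overall and by 100% at that facility. With full consent the gap is zero.

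**The case against.** The strongest reply is that much of this may be handled outside the protocol. Containers are to be labelled and a storage SOP is promised, which could well require separation. The confidentiality rule bars identifiers, not a mark showing that a cassette came from an excluded group. This stands to the extent that a reader might infer that the cassettes share one container and can never be separated; the protocol does not say so. What remains is that it describes no separating step, while its storage instruction and the supervisors' check both cover all used RDTs.

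A reader might also infer that the TPR comparison is biased by design. The documents do not support that: the gap is zero under equal positivity, and the documents give no positivity for the unmatched tests.

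Nor is there a clear contradiction over in-patients. The exclusion bullet reads naturally as concerning CHW tests only, which leaves the facility inclusion line intact. The loose end is that the facility target is described as outpatient tests. The non-consent gap exists only if someone refuses, and all workers are to be approached.

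The ACT comparison is a secondary outcome, and a stable offset would largely cancel in month-to-month change. Both are true. The offset does not cancel in the monthly levels that are compared and fed back, nor in any test of whether counts and consumption converge. The primary outcome row already refers to RDT counts and RDT positives, so microscopy is a problem for the ACT row, not an established one for TPR.

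**Conclusion.** The point holds in two parts, with moderate confidence.

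- The CHW exclusion has no described means of being applied at the count. Left in, the cassettes inflate CHW volume against DHIS2 by q/(1−q): 5.3% to 17.6% for assumed shares of 5% to 15%. Taken out, the mismatch moves to RDT consumption and possibly to ACTs.
- The facility ACT comparison shows an excess of m/(1−m) under the rule the protocol itself describes: 11% at an assumed 10% microscopy share and 45% at 31%, with equal positivity. The district share is unknown.

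The damage is mainly to volume and ACT comparisons. These mismatches could not by themselves produce the hypothesised differences of 25 points (facilities) and 45 points (CHWs). Non-consent and the in-patient wording are secondary: the first is conditional, the second a clarification. What goes into which container should be settled before collection, because a mixed pile is hard to sort afterwards.

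**What to change.** 1. Have CHWs keep cassettes from pregnant women in a separate marked bag and count them apart. Leave them out of the DHIS2 comparison, include them in the RDT and ACT consumption comparison, and include them in the register comparison where the register lists them. Cost: a second labelled bag per CHW (31) and a line in the storage SOP. A group mark on a bag identifies no patient.
2. At health facilities, compare ACTs with RDT positives plus microscopy positives from the register. Registers are already copied or brought for the count, and the Appendix 1 page has columns for investigations requested and their results. Cost: one more tally in the monthly extraction.
3. If any facility worker declines, restrict the DHIS2 volume comparison to facility-months in which all testers participate. Selecting participants' register lines is less secure, because the Appendix 1 columns shown do not identify the tester.
4. Reconcile the outpatient wording in Study population, the facility inclusion line and the in-patient reference in the exclusion bullet, so that one rule applies to every source. Check first whether DHIS2 can be split by in-patient status; the documents do not say.
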